10.5. Appendix 5: Genetics

Use/Analysis of DNA

- Genetic variation may impact a participant's response to study intervention, susceptibility to, and severity and progression of disease. Therefore, where local regulations and IRBs/ECs allow, a blood sample will be collected for DNA analysis.
- The scope of the genetic research may be narrow (eg, 1 or more candidate genes) or broad (eg, the entire genome), as appropriate to the scientific question under investigation.
- The samples may be analyzed as part of a multistudy assessment of genetic factors involved in the response to PF-07209960 or study interventions of this class to understand treatments for the disease(s) under study or the disease(s) themselves.
- The results of genetic analyses may be reported in the CSR or in a separate study summary, or may be used for internal decision making without being included in a study report.
- The sponsor will store the DNA samples in a secure storage space with adequate measures to protect confidentiality.
- The samples will be retained as indicated:
 - Samples for banking will be stored indefinitely or for another period as per local requirements.
 - Participants may withdraw their consent for the storage and/or use of their Banked Biospecimens at any time by making a request to the investigator; in this case, any remaining material will be destroyed. Data already generated from the samples will be retained to protect the integrity of existing analyses.
 - Banked Biospecimens will be labeled with a code. The key between the code and the participant's personally identifying information (eg, name, address) will be held at the study site and will not be provided to the sample bank.

10.6. Appendix 6: Liver Safety: Suggested Actions and Follow-up Assessments

Potential Cases of Drug-Induced Liver Injury

Humans exposed to a drug who show no sign of liver injury (as determined by elevations in transaminases) are termed “tolerators,” while those who show transient liver injury, but adapt are termed “adaptors.” In some participants, transaminase elevations are a harbinger of a more serious potential outcome. These participants fail to adapt and therefore are “susceptible” to progressive and serious liver injury, commonly referred to as DILI. Participants who experience a transaminase elevation above $3 \times$ ULN should be monitored more frequently to determine if they are an “adaptor” or are “susceptible.”

LFTs are not required as a routine safety monitoring procedure in this study. However, should an investigator deem it necessary to assess LFTs because a participant presents with clinical signs/symptoms, such LFT results should be managed and followed as described below.

In the majority of DILI cases, elevations in AST and/or ALT precede TBili elevations ($>2 \times$ ULN) by several days or weeks. The increase in TBili typically occurs while AST/ALT is/are still elevated above $3 \times$ ULN (ie, AST/ALT and TBili values will be elevated within the same laboratory sample). In rare instances, by the time TBili elevations are detected, AST/ALT values might have decreased. This occurrence is still regarded as a potential DILI. Therefore, abnormal elevations in either AST OR ALT in addition to TBili that meet the criteria outlined below are considered potential DILI (assessed per Hy’s law criteria) cases and should always be considered important medical events, even before all other possible causes of liver injury have been excluded.

The threshold of laboratory abnormalities for a potential DILI case depends on the participant’s individual baseline values and underlying conditions. Participants who present with the following laboratory abnormalities should be evaluated further as potential DILI (Hy’s law) cases to definitively determine the etiology of the abnormal laboratory values:

- Participants with AST/ALT and TBili baseline values within the normal range who subsequently present with AST OR ALT values $>3 \times$ ULN AND a TBili value $>2 \times$ ULN with no evidence of hemolysis and an alkaline phosphatase value $<2 \times$ ULN or not available.
- For participants with baseline AST **OR** ALT **OR** TBili values above the ULN, the following threshold values are used in the definition mentioned above, as needed, depending on which values are above the ULN at baseline:
 - Preexisting AST or ALT baseline values above the normal range: AST or ALT values >2 times the baseline values AND $>3 \times$ ULN; or $>8 \times$ ULN (whichever is smaller).

- Preexisting values of TBili above the normal range: TBili level increased from baseline value by an amount of at least $1 \times \text{ULN}$ **or** if the value reaches $>3 \times \text{ULN}$ (whichever is smaller).

Rises in AST/ALT and TBili separated by more than a few weeks should be assessed individually based on clinical judgment; any case where uncertainty remains as to whether it represents a potential Hy's law case should be reviewed with the sponsor.

The participant should return to the investigator site and be evaluated as soon as possible, preferably within 48 hours from awareness of the abnormal results. This evaluation should include laboratory tests, detailed history, and physical assessment.

In addition to repeating measurements of AST and ALT and TBili for suspected cases of Hy's law, additional laboratory tests should include albumin, CK, direct and indirect bilirubin, GGT, PT/INR, total bile acids, and alkaline phosphatase. Consideration should also be given to drawing a separate tube of clotted blood and an anticoagulated tube of blood for further testing, as needed, for further contemporaneous analyses at the time of the recognized initial abnormalities to determine etiology. A detailed history, including relevant information, such as review of ethanol, acetaminophen/paracetamol (either by itself or as a coformulated product in prescription or over-the-counter medications), recreational drug, supplement (herbal) use and consumption, family history, sexual history, travel history, history of contact with a jaundiced person, surgery, blood transfusion, history of liver or allergic disease, and potential occupational exposure to chemicals, should be collected. Further testing for acute hepatitis A, B, C, D, and E infection and liver imaging (eg, biliary tract) and collection of serum samples for acetaminophen/paracetamol drug and/or protein adduct levels may be warranted.

All cases demonstrated on repeat testing as meeting the laboratory criteria of AST/ALT and TBili elevation defined above should be considered potential DILI (Hy's law) cases if no other reason for the LFT abnormalities has yet been found. **Such potential DILI (Hy's law) cases are to be reported as SAEs, irrespective of availability of all the results of the investigations performed to determine etiology of the LFT abnormalities.**

A potential DILI (Hy's law) case becomes a confirmed case only after all results of reasonable investigations have been received and have excluded an alternative etiology.

10.7. Appendix 7: ECG Findings of Potential Clinical Concern

ECG Findings That May Qualify as AEs

 Marked sinus bradycardia (rate <40 bpm) lasting minutes. New PR interval prolongation >280 msec. New prolongation of QTcF to >480 msec (absolute) or by 60 msec from baseline. New-onset atrial flutter or fibrillation, with controlled ventricular response rate: ie, rate <120 bpm. New-onset type I second-degree (Wenckebach) AV block of >30 seconds' duration. Frequent PVCs, triplets, or short intervals (<30 seconds) of consecutive ventricular complexes.
ECG Findings That May Qualify as SAEs

 QTcF prolongation >500 msec. New ST-T changes suggestive of myocardial ischemia. New-onset left bundle branch block (QRS >120 msec). New-onset right bundle branch block (QRS >120 msec). Symptomatic bradycardia. Asystole: 
 In awake, symptom-free participants in sinus rhythm, with documented periods of asystole >3.0 seconds or any escape rate <40 bpm, or with an escape rhythm that is below the AV node. In awake, symptom-free participants with atrial fibrillation and bradycardia with 1 or more pauses of at least 5 seconds or longer. Atrial flutter or fibrillation, with rapid ventricular response rate: rapid = rate >120 bpm. Sustained supraventricular tachycardia (rate >120 bpm) ("sustained" = short duration with relevant symptoms or lasting >1 minute).

- Ventricular rhythms >30 seconds' duration, including idioventricular rhythm (heart rate <40 bpm), accelerated idioventricular rhythm (HR >40 bpm to <100 bpm), and monomorphic/polymorphic ventricular tachycardia (HR >100 bpm (such as torsades de pointes)).
- Type II second-degree (Mobitz II) AV block.
- Complete (third-degree) heart block.

ECG Findings That Qualify as SAEs

- Change in pattern suggestive of new myocardial infarction.
- Sustained ventricular tachyarrhythmias (>30 seconds' duration).
- Second- or third-degree AV block requiring pacemaker placement.
- Asystolic pauses requiring pacemaker placement.
- Atrial flutter or fibrillation with rapid ventricular response requiring cardioversion.
- Ventricular fibrillation/flutter.
- At the discretion of the investigator, any rhythmia classified as an adverse experience.

The enumerated list of major events of potential clinical concern are recommended as "alerts" or notifications from the core ECG laboratory to the investigator and Pfizer study team, and not to be considered as all-inclusive of what to be reported as AEs/SAEs.

10.8. Appendix 8: Detailed Dose Escalation/De-escalation Scheme for BLRM Design

An adaptive Bayesian design using EWOC will guide the dose escalation for PF-07209960. The use of Bayesian response adaptive designs for Phase 1 studies has been advocated for and is one of the key elements of the FDA's Critical Path Initiative ([Rogatko et al, 2007](#); [Neuenschwander et al, 2015](#)).

The BLRM will be set-up for the dose-toxicity relationship of PF-07209960 when administered as a single agent. This Bayesian analysis will be based on DLT data (absence or presence of DLT) during the first cycle (DLT observation period) accumulated throughout the dose escalation. This appendix provides details of the statistical models. The derivation of prior distributions, general description of MAP approach (in the event that alternative IV dosing is used), performance check of the model, some hypothetical dose escalation scenarios, and operating characteristics are presented in a technical supplement to this appendix.

10.8.1. Statistical Models

10.8.1.1. Prior Specifications for monotherapy BLRM

In the dose escalation Part 1, the DLT relationship will be described by a 2-parameter BLRM formulated as follows:

$$\text{logit}(\pi(d)) = \log(a) + \beta \log\left(\frac{d}{d^*}\right)$$

Where, $\pi(d)$ is the probability that a participant has a DLT during the first cycle (28 days) when PF-07209960 is given as single agent. The parameter d^* is the reference dose in the model and is used to scale the doses of PF-07209960. The $a, \beta > 0$ are the parameters of the model such that $a (>0)$ is the PF-07209960 odds of a DLT at d^* ; and $f3 (>0)$ is the increase in the log-odds of a DLT by a unit increase in log-dose.

The Bayesian approach requires the specification of prior distributions for the model parameters $\log(a)$ and $\log(f3)$. Available preclinical toxicology makes it difficult to predict toxicity profile of PF-07209960 single agent in humans. For this reason, the priors of the model parameter distribution are defined using a weakly informative prior. This approach allows for considerable uncertainty, so that the a-priori range for the parameters covers a wide range of plausible values.

Meta-Analytic-Predictive Priors Approach

A MAP prior may be used to define the prior for any or all of the treatment arms in the dose escalation in order to account for heterogeneity between the available DLT data and the actual study protocol population and treatment regimen/schedule. For example, if alternative IV dosing is used a MAP prior may be used to incorporate SC dosing data. Furthermore, a

MAP prior maybe used instead of, or in addition to a weakly informative prior to form a weighted mixture prior and account for uncertainty. A mixture prior can take the form

$$p \times BVN_{MAP} + (1 - p) \times BVN_{Weak}$$

The weights of the mixture prior are driven by clinical judgement. The aim of the MAP prior approach for treatment i is to derive a prior distribution for the logistic parameters $(\log(a_i^*), \log(f\beta_i^*))$ using prior DLT data, available from previously conducted trial, or from the same study but with another regimen.

Let r_i and n_i be the number of participants with a DLT, and the total number of participants at dose d_i in the DLT data available from the historical trial. The corresponding probability of a DLT is rr_{di} . The model specifications are as follows:

$$\begin{aligned} r_i/rr_{di} &\sim Bin(rr_{di}, n_i) \\ ogit(rr_{di}) &= \log(a_i) + f\beta_i \log\left(\frac{d_i}{d_i^*}\right) \\ (\log(a_i), \log(f\beta_i)) &/ \mu, 1/ \sim BVN(\mu_i, 1/i) \\ (\log(a_i^*), \log(f\beta_i^*)) &/ \mu, 1/ \sim BVN(\mu_i, 1/i) \end{aligned}$$

The parameter $\mu_i = (\mu_{i1}, \mu_{i2})$ is the mean for the logistic parameter, and $1/i$ is the between-regimen/study covariance matrix. Covariance matrix $1/i$ is defined by the standard deviations of (t_{i1}, t_{i2}) , and correlation r_i .

The following priors will be used for these parameters:

- normal priors for μ_{i1} and μ_{i2} ;
- log-normal priors for t_{i1} and t_{i2} ;
- a uniform prior for r_i .

To further specify the details of these distributions the principles described in [\(Neuenschwander et al, 2015\)](#) will be followed. The MAP prior for model parameters of PF-07209960, is the predictive distribution.

$$(\log(a_i^*), \log(f\beta_i^*))/\left(r_i, n_i\right)$$

Since the predictive distribution is not available analytically, the MCMC method is used to simulate values from this distribution. This is implemented using JAGS version 4.10.

Sensitivity Analysis

Despite being prespecified in the protocol, some AEs that fall into the category of DLTs may need to be considered differently. Conversely, some AEs that are not defined as a DLT per protocol should be considered by the dose escalation BLRM. Accordingly, the new concept

of an “equivocal” DLT or AE is introduced: most AE/DLTs are considered “unequivocal,” but certain types of AEs/DLTs are considered to be “equivocal.” To mitigate the risk of dichotomizing and misclassifying DLTs, the sensitivity analysis that uses those weighted equivocal DLT/AE data into the BLRM model estimation will also be performed. The BLRM model uses all the equivocal and unequivocal AE/DLT data, but the variability associated with equivocal AEs/DLTs (less interpretable) is increased. So, the model recommendations are more heavily weighted towards unequivocal data. See below for the posterior distribution of the BLRM model parameters based on the theory of power prior.

Suppose n participants treated at dose d with m unequivocal DLTs and r equivocal DLTs/AEs, and the weight w for the equivocal data, then based on the power prior,

$$\begin{aligned} Posterior(a, f3/d, m, r, w) &\propto L(m/a, f3, d, w) \times L(r/a, f3, d, w) \times prior(a, f3) \\ &\propto p(a, f3, d)^m \times [1 - p(a, f3, d)]^{n-r-m} p(a, f3, d)^{rw} \times prior(a, f3), \end{aligned}$$

Where L is the likelihood of the observed DLT data, and $p(a, f3, d)$ is the probability of DLT at dose d that is modeled by logistic regression in BLRM. To achieve the equality sign, approximate normalizing constant is required. The contribution of equivocal AEs/DLTs to the data (likelihood) and the Bayesian posterior estimation of the MTD are weighted; the weight parameter controls the influence and can be interpreted as a precision parameter for equivocal AE/DLT data, similar to the scale parameter in the power prior for the Bayesian historical borrowing. The weight for an equivocal DLT is decreased (eg, 1 decreased to 0.5) and the weight for an equivocal AE (non-DLT by protocol) is increased (eg, 0 increased to 0.5). To maintain the integrity of a trial, the weights pre-specified as 0.5 in the analysis. If all the investigators and the sponsor agree on the equivocal DLT/AE data, the DLT weighting approach could be the primary dose escalation method. This DLT weighting approach provides a flexible and powerful tool that may incorporate the clinician’s valuable experience with some specific DLTs/AEs and improve MTD estimation in dose-escalation trials.

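### Protocol Appendix 8: the printed weighted likelihood loses the non-DLT share of an equivocal AE that is not a DLT by protocol

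*Protocol*

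**What the plan says.** The ordinary model in Protocol Appendix 8 rests on "DLT data (absence or presence of DLT) during the first cycle". A participant without a DLT therefore contributes (1-p), where p is the DLT probability at the dose.

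The Sensitivity Analysis text in section 10.8.1.1 adds equivocal events. Some protocol DLTs are to count for less, and in the other direction "some AEs that are not defined as a DLT per protocol should be considered by the dose escalation BLRM". With n participants at a dose, m unequivocal DLTs and r equivocal events of either kind, the likelihood is p^m times a term printed as "1 - p(a, f3, d)]^{n-r-m} p(a, f3, d)^{rw" (a fragment; β appears as f3 in the extracted text). In full this is `p^m (1-p)^(n-r-m) p^(rw)`.

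One weight w serves both kinds of event. For an equivocal DLT it goes from 1 down to 0.5. For the other kind, "the weight for an equivocal AE (non-DLT by protocol) is increased (eg, 0 increased to 0.5". The appendix has "the weights pre-specified as 0.5 in the analysis". It describes the effect in three statements: "the variability associated with equivocal AEs/DLTs (less interpretable) is increased"; "the model recommendations are more heavily weighted towards unequivocal data"; and the weight "can be interpreted as a precision parameter for equivocal AE/DLT data".

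Protocol 9.4.1.1 and SAP 5.1 say that this analysis will be performed and could become the primary escalation method if all investigators and the sponsor agree. The SAP gives no formula of its own and refers back to Appendix 8.

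**The concern.** Formula and text describe different things for one of the two event types. An equivocal AE is by definition not a DLT under the protocol, and its stated starting weight is 0. The natural meaning of that starting point is the ordinary analysis, in which the participant counts as a non-DLT. The printed formula takes every equivocal participant out of the non-DLT exponent and puts back only a power of p.

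A programmer who follows the printed line would enter protocol non-DLTs as DLT evidence only. Cohorts are about 2-4 participants (Protocol 9.2.1), so one lost non-DLT is a noticeable part of the data at a dose. The result feeds the rule that a dose is usable only if the risk of overdosing is below 25% (Protocol 4.3.2).

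**Working it through.** **Inputs.** The likelihood, weights and definitions of n, m and r are from Appendix 8. The DLT-rate bounds 0.16 and 0.33 are from Protocol 4.3.4, and the 25% limit is from 4.3.2. The prior values and the reference dose d* are not given in the documents.

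**Step 1: the two stated starting weights.**
- w = 1 (equivocal DLT): the formula gives `p^(m+r) (1-p)^(n-m-r)`, the ordinary likelihood with r more DLTs. This reproduces the text.
- w = 0 (equivocal AE): the formula gives `p^m (1-p)^(n-r-m)`. The ordinary likelihood is `p^m (1-p)^(n-m)`, so a factor (1-p)^r is missing. With n=6, m=0, r=2 the data become 0 in 4 instead of 0 in 6. No w ≥ 0 turns p^w into (1-p).

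**Step 2: the pre-specified weight 0.5.** Two equivocal AEs give p^(2×0.5) = p, which is 1 DLT in 1 participant. A fractional event, p^w (1-p)^(1-w) each, gives p(1-p), which is 1 in 2. Crude rates for n=6, r=2:

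| m | Protocol classification | Printed | Share restored |
|---|---|---|---|
| 0 | 0/6 | 1/5 = 0.200 | 1/6 = 0.167 |
| 1 | 1/6 = 0.167 | 2/5 = 0.400 | 2/6 = 0.333 |

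**Step 3: prior-free size.** The likelihood ratio for p=0.33 against p=0.16 is (0.33/0.16)^events × (0.67/0.84)^non-events, that is 2.0625^events × 0.7976^non-events.

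| Equivocal AEs | Protocol non-DLT | Printed, w=0.5 | Share restored |
|---|---|---|---|
| 1 | 0.80 | 2.0625^0.5 = 1.44 | 1.44 × 0.7976^0.5 = 1.28 |
| 2 | 0.64 | 2.06 | 2.0625 × 0.7976 = 1.65 |
| 3 | 0.51 | 2.96 | 2.11 |

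One equivocal AE at printed weight 0 gives 1.00, where the protocol non-DLT gives 0.80. A full DLT gives 2.06.

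**Step 4: other forms.** The text does not fix the form at 0.5. Two others also return (1-p) at weight 0. The mixture w·p + (1-w)(1-p) gives (0.5×0.33 + 0.5×0.67)/(0.5×0.16 + 0.5×0.84) = 1.00 for one AE. Using √w as the event exponent gives 2.0625^0.707 × 0.7976^0.293 = 1.56. The printed 1.44 lies between these two.

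**Step 5: illustration against the 25% limit, under assumed priors.** The two-parameter model was integrated on a grid. Assumptions: SD 2 for log(α) and 1 for log(β); median DLT risk at d* of 0.33 or 0.25; d* at, half a log above or one log above the current dose; 0/3 and 0/3 at the two half-log lower doses. All equivocal events are taken as AEs, with n = 2, 3, 4 or 6. That is 40 outcomes in each of 6 settings, 240 in all. The figures are counts of outcomes, not probabilities.
- Printed against share-restored: 24 of 240 exceed 25% only as printed, and none the other way. For n = 2-4 it is 12 of 114; with one equivocal event, 5 of 90. Of the 24, 19 need two or more equivocal events.
- Other assumed SD pairs give roughly 21 to 29 of 240, depending on the pair and the grid.
- Printed against the mixture: 74 of 240. Against √w: 0, with 6 the other way.
- Printed at weight 0 against the ordinary model: 38 of 240, which needs no choice of form at 0.5.
- Median rise in the overdose probability, printed over share-restored: 0.03-0.05 for one equivocal AE and 0.06-0.10 for two.
- Example (median 0.33, d* half a log above): n=2, r=2, m=0 gives 0.343 printed, 0.237 share-restored and 0.024 in the ordinary model.

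**The case against.** The strongest defence is that the formula is a power-prior discount and does what such a discount does. The appendix invokes the power prior, speaks of more variability for equivocal data and calls w a precision parameter. Under a power prior, weight 0 removes a datum. On this reading, the 0 in the text is only the AE's weight as DLT evidence, it is never run, and the gap is one of wording.

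This stands for equivocal DLTs, where p^w discounts a DLT that occurred. It does not carry over to equivocal AEs. A power prior discounts the observed outcome, which here is a non-DLT by protocol, whereas the formula discounts a DLT that the protocol says did not occur.

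A reader might infer that the error is two protocol non-DLTs adding up to one full DLT. The documents do not support that: the total follows from raising the weight to 0.5, and it is the same with the share restored. Only the lost non-DLT share is wrong.

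It is also fair that no document fixes the form at 0.5 and that the counts against the 25% limit move with the comparison form. The prior derivation and operating characteristics are in a technical supplement that was not available. Finally, restoring the share gives an equivocal AE full observation weight, which conflicts with the discounting language unless that language is narrowed.

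**Conclusion.** The concern holds for equivocal AEs that are not DLTs by protocol. The printed likelihood deletes them at their stated starting weight and, at 0.5, enters them with no non-DLT share. This is algebra on the printed expression and needs no prior. The expression is complete as it stands, so a term lost in text extraction is unlikely.

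The effect overstates DLT risk relative to both the protocol classification and the share-restored form, and against the latter it is usually small. It matters mainly for borderline 25% decisions with two or more equivocal AEs at one dose. The Step 5 counts are illustrations only.

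Two stronger conclusions should not be drawn. Toxicity is not under-called relative to the protocol's own DLT count. Nor does a crossing of 25% by itself mean a changed dose: the weighting is a sensitivity analysis unless adopted by agreement, and the dose level review may choose a dose at or below the model's recommendation (Protocol 9.6). The mismatch should still be corrected before the model is programmed, because the method could become primary.

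**What to change.** Count equivocal DLTs (rD) and equivocal AEs (rA) separately and use a likelihood that returns (1-p) for an AE at weight 0, for example `p^(m + w·rD + w·rA) (1-p)^(n - m - rD - w·rA)`. Equivocal DLTs keep the printed p^w discount. An equivocal AE gives (1-p) at weight 0 and p^0.5 (1-p)^0.5 at weight 0.5.

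The downside is that its exponents then sum to 1, a full observation. The statements on increased variability, on heavier weighting of unequivocal data and on w as a precision parameter must therefore be limited to equivocal DLTs. The operating characteristics in the technical supplement should be rechecked for scenarios with equivocal AEs.

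If the printed form is kept on purpose, Appendix 8 should say that an equivocal AE enters as a down-weighted DLT with no non-DLT share, and that weight 0 removes the participant.

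The cost of the change is one formula, three statements in Appendix 8, a record of whether each equivocal event is a DLT by protocol, and the matching likelihood in the analysis code. The code and the supplement were not available, so the effort of the recheck is unknown.
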